16.3 Subject Self-Assessment

SUBJECT SELF ASSESSMENT

SUBJECT NUMBER:						SUBJECT INITIALS:					
VISIT DATE:											
	D	D	М	М	М	Y	Y	Υ	Y		
		. o .fp	,, ,	W 1: 0				** 7	*** ** #	.	
Visit Number		it 2 [Bas	eunej		[Follow Up]		Visit 4 [Follow Up] Vis		'		Study Visit
Visit Day		Day 1		Da	y 2		Day 8			Day 1	5
nis assessment is oplication of the	otion. P	lease rate	e the ex	perience ii		below.				ceu an	ter tile
Score		Grade					Check one				
0		None			Т						
1		Mild		0	ccasional ep						
2		Moderat	e		Frequent, several times a day, bothersome.						
3		Severe			Nearly cons						
				STIN	GING/BU	RNINC	j				
(Se	ensation	of the sk	in is pai	nfully hot	or noticeabl	e tinglin	g sensatio	n in the	last 24 h	ours)	
Score		Grade			Definition						check one
0		None			Absent						
1	Mild				Slight, barely present						
2		Moderat	e		Distinct presence						
3		Severe			Marked, intense						
ubject and/or C	aregiver	(Initials):			_	Dat	:e			
ompleted & Rev	viewed (By (Initia	ls):				Dat	:e			

16.4 Site Assessment

SITE ASSESSMENT

SUBJECT NUMBER:								SUBJECT INITIALS:			
VISIT DATE:											
	D	D	М	М	M	Y	Υ	Υ	Υ		
SITE PERSONNE	L TO COMPLI	ETE:									
1. Head Lice Eva	luation mini	mum of 1	5 minutes	:							
Live Ac	dult Lice Prese	ent:	Yes 🗌	No Nu	umber of	:					
Live Ny	mphs Preser	nt:	Yes 🗌	No Nu	umber of	:					
2. Skin/Scalp Irr	itation Asses	sment (in	clude fore	head, ne	ck and ea	ırs):					
					Тур	oe of Irritatio	on				
Rating	Rating Pruritus= Itching Erythema= Redness o the scalp						= Breaking of ally caused ratching		Pyoderma= Sores filled with clear fluid, pus or crusting		
None = 0	The scalp ditch.	oes not	No rec scalp.	lness of th	ne	No broken s	skin on the		No lesions visible on the scalp.		
Mild = 1	Occasional of itching, r	not	Faint, percep with li distrib	otible eryt mited	hema	One or two scalp on wh broken.		\	One or two lesions visible with crusting or other evidence of infection.		
Moderate = 2	e = 2 Frequent, several Diffuse pink areas of times a day, scalp are readily bothersome. visible.					More than to areas of the broken skin generalized	scalp with but not	l c scalp. b	Presence of more than two lesions with crusting or other evidence of infection, but not generalized across the scalp.		
Severe = 3	Nearly cons frequent so very bother	ratching,	_	areas of th	ne	Widespread breaking of the skin involving most of the scalp.			Lesions with crusting or other evidence of infection, involving most of the scalp.		
Pruritu	ıs Score= _										
Erythe	ma Score= _										
Excoria	ation Score=_										
Pyoder	rma Score= _										
3. Ocular Irrita	tion Assessm	ent:									
Eye irri	itation preser	nt:	Yes [No							
Conjun	ictivitis prese	nt:	Yes	No							
Ocular	Hyperemia p	resent: [Yes [☐ No							
Completed By (Initials):		Date_

APPENDIX C: SKIN/SCALP IRRITATION ASSESSMENT	

APPENDIX D: OCULAR IRRITATION ASSESSMENT

1. INTRODUCTION

This document describes the statistical methods and data presentations to be used in the summary and analysis of data from Protocol MAP-7189. Background information is provided for the overall study design and objectives. The reader is referred to the study protocol and electronic case report forms (eCRFs) for details of study conduct and data collection.

1.1. Study Overview

Clinical protocol MAP-7189 is a Randomized, Multi-Center, Double-blind, Placebo Controlled, Parallel Group Trial to Evaluate Efficacy and Safety of Mayne Pharma's Ivermectin 0.5% Lotion Compared to Sklice® Ivermectin 0.5% Lotion in the Treatment of Head Lice. The primary objective of the study is to establish the efficacy of a single application of Ivermectin 0.5% lotion in the treatment of head lice under at-home use conditions compared with Sklice® 0.5% lotion, and to demonstrate that both active lotions have superior efficacy compared to Placebo.

The study also assesses comparative safety of Ivermectin 0.5% Lotion (Mayne Pharma, LLC) and Sklice® Ivermectin 0.5% Lotion and local tolerability of Ivermectin 0.5% Lotion.

The subject population includes healthy male and female subjects aged 6 months to 18 years who are infested with Pediculus humanus capitis. The youngest infested household member will be considered the index subject. Household members, up to a maximum of 3 members, infested with an active head lice infestation defined as at least 1 live louse (adult and/or nymph) present on the scalp and/or hair, as determined by a trained evaluator will receive treatment with an over-the-counter head lice treatment product at baseline.

The study is comprised of three phases: Screening, Treatment, and Follow-Up. The duration of this study is 15 days (+/- 3). The Screening Phase is Day -1-0. The Treatment Phase is Day 1. Preferably, screening and treatment will occur on the same day. The Final Study Visit is on day 15 (+/- 3 days) following administration of the study product.

Potential subjects will be screened and the index subject will be eligible for enrollment into the study. During the baseline visit (Day 1), which can occur on the same day as screening (Day 0), the Investigator will record subject's demographics, medical history, review concomitant medication, identifying any prohibited therapies the subject may receive, perform physical examination, collect vital signs and perform urine pregnancy test.

Eligible subjects will be randomized in a ratio of 3:3:1 to receive either the Mayne Pharma's Ivermectin 0.5% lotion, Sklice® 0.5% lotion, or placebo lotion treatment and will be trained on the application of the study drug and subject's diary completion. Infested household members, up to 3 members per household, will be treated with an over-the-counter head lice treatment product on-site.

The study drug will be applied as a single, at-home dose. Subjects will be instructed to apply a full tube amount (4 oz.) of Ivermectin 0.5% lotion to fully coat dry hair and scalp, avoiding the

eyes and mucus membranes. The lotion will be left on the hair and scalp for 10 minutes, then rinsed off with warm water. The tube is intended for a single use; all used tubes should be returned at the second visit (first follow-up visit) to the clinical site for product accountability. In addition to receiving the study drug, the index subjects and household members will be instructed on an overall lice management program, which includes:

- Wash (in hot water) or dry-clean all recently worn clothing, hats, used bedding and towels.
- Wash (in hot water) personal care items such as combs, brushes and hair clips.
- A fine-tooth comb or special nit comb may be used to remove dead lice and nits after treatment.

Index subjects will return for post-baseline visits assessments at Days 2, 8, and 15, returning used tubes of the study drug at Day 2, which will be accounted for along with diary cards, which will be reviewed by the site personnel for completeness. The Investigator will perform a visual assessment for the presence or absence of head lice, record local application site reactions, and perform an ocular irritation assessment. The site will provide a Subject Self-Assessment worksheet to record tolerability of treatment. Urine pregnancy testing will be performed at the Screening Visit and the Final Study Visit, with interim visits confirming pregnancy has not occurred through questioning of the index subject.

Final efficacy, safety and tolerability assessments will occur at visit 5 (Day 15±3). Subjects will be encouraged to report any complications or adverse effects during their participation.

1.2. Time and Events Schedule

Visit Number	Visit 1 Screening ¹	Visit 2 Baseline ²	Visit 3 Follow-up	Visit 4 Follow-up	Visit 5 EOS/ET ³
Visit Day	Day -1 to 0	Day 1	Day 2 ⁴	Day 8 (±2)	Day 15 (±3)
Informed Consent	Х				
Eligibility Criteria	Х				
Subject Demographics	X				
Medical History	Х				
Physical Examination	X ⁵				
Investigational Product Dispensation/Randomization		X ⁶			
Vital Signs ⁷		Х			X
Urine Pregnancy Test ⁸	Х				X
Head Lice Visual Assessment	X ⁹	X ⁹	X	Х	X
Household Members Standard of Care Treatment		Х			
Local Skin/Scalp Irritation Assessment			X	X	X
Ocular Irritation Assessment			X	Х	X
Subject Self-Assessment		Х	X	Х	X
Investigational Product Accountability			X		
Subject Diary Dispensation		Х			
Subject Diary Collection and Compliance Review			X		
Concomitant and Prohibited Medication Review	X	X	X	X	Х
Adverse Events Assessment			X ¹⁰	Х	Х

TABLE 1.2 Study Procedures and Assessments.

¹Rescreening will be permitted for out of window index subjects and those subjects whose household members cannot accompany them at their initial screening visit. 2 visit 2 (baseline) may be completed on the same day as visit 1 (screening). If screening and baseline are completed on the same day, assessments performed on both screening and baseline need only be performed once. Refer to section 7. Study procedures and schedule of events for details and restrictions.

³ index subjects identified as treatment failures will be terminate early from the study and be provided the standard of care rescue treatment.

⁴ must be within 24 hours of treatment.

⁵ physical examinations are to be performed if inclusion/exclusion criteria are satisfied at screening.

⁶ prior to randomization, the investigator must confirm the subject still meets all inclusion/exclusion criteria. ⁷ vital signs will include body temperature, heart rate and blood pressure (systolic and diastolic). Blood pressure and heart rate will be measured after the subject has been sitting restfully for at least 5 minutes.

⁸ for female index subjects of child-bearing potential.

⁹ for both index subjects and infested household members.

¹⁰AE reporting period for this study begins upon receiving the first application of investigational product and ends at the final protocol required visit.

1.3. Glossary of Terms

AE	Adverse Event
CFR	Code of Federal Regulations
CMP	Clinical Monitoring Plan
CRA	Clinical Research Associate
CRF	Case Report Form
CRO	Contract Research Organization
eCRF	Electronic Case Report Forms
EOS	End of Study
ET	Early Termination
FDA	Food and Drug Administration
GCP	Good Clinical Practice
IB	Investigator's Brochure
ICF	Informed Consent Form
ICH	International Conference on Harmonisation
IEC	Independent Ethics Committee
IMV	Interim Monitoring Visit
IRB	Investigational Review Board
ITT	Intent to Treat
LOCF	Last Observation Carried Forward
Mayne	Mayne Pharma, LLC/ Mayne Pharma International Pty Ltd
MedDRA	Medical Dictionary for Regulatory Activities
mITT	Modified Intent-to-Treat
MRT	Mean Residence Time
OTC	Over the Counter
PI	Principal Investigator
PMH	Past Medical History
PP	Per-Protocol
QA	Quality Assurance
QC	Quality Control
SAE	Serious Adverse Event
SAP	Statistical Analysis Plan
SAS	Statistical Analysis System
SD	Standard deviation
SOC	System Organ Class
SOP	Standard Operating Procedure
SUSAR	Suspected Unexpected Serious Adverse Event
TEAE	Treatment Emergent Adverse Event
US	United States

2. OBJECTIVES

The primary objective of this study is:

- To establish the efficacy of a single application of Ivermectin 0.5% lotion in the treatment of head lice (Pediculus humanus capitis) under at-home conditions compared with Sklice® 0.5% lotion
- To demonstrate that both active lotions have superior efficacy compared to Placebo

The secondary objective of this study is:

• To demonstrate comparative safety and local tolerability of Ivermectin 0.5% lotion (Mayne Pharma, LLC) vs Sklice® 0.5% lotion.

3. GENERAL STATISTICAL CONSIDERATIONS

3.1. Sample Size Estimation

Under the assumption that the Test and Reference treatments are equally efficacious with a true cure rate of at least 67%, and that the placebo has a true cure rate no greater than 27%, computer simulations were performed to determine the probability (power) of study success for different sample sizes. Study success in a simulated trial was defined as having the 90% continuity-corrected confidence interval in the PP population for the Test-to-Reference difference in cure proportions be contained in the bioequivalence interval [-0.20, +0.20] at the same time that both active treatments were demonstrated in the mITT population to have cure rates that were greater than, and statistically different (p<0.05) from, that of the placebo. It was assumed that approximately 90% of the mITT subjects would qualify as PP ones.

It was determined that for at least an 80% probability of study success, 280 mITT index subjects would be needed (120:120:40; Test: Reference: Placebo) to obtain 252 PP ones (108:108:36; Test: Reference: Placebo).

3.2. Randomization

This is a double-blind study, thus all site staff, study monitor, and subjects will be blinded to the randomization scheme except for the Unblinded Site Personnel/ designee and Unblinded Monitor. Furthermore, the randomization scheme will be retained by the Drug Depot and will only be shared with Unblinded Site Personnel or designee.

The actual treatment given to individual subjects is determined by a computerized block randomization scheme prepared by an independent third party. The independent third party will prepare the randomization list and hold it throughout the conduct of the study. Subjects are randomized on a 3:3:1 basis (test drug: active comparator: placebo) and stratified by clinical site.

After signing the Informed Consent, each subject will be assigned a unique subject number. Subjects are identified using subject initials, subject number, and date of birth. The subject numbers will be generated by the EDC and assigned sequentially in the order in which subjects are consented at each center.

If a subject discontinues from the study, the subject number and randomization number are not to be reused, and the subject is not allowed to re-enter the study.

The randomization scheme for treatment allocation will be used for statistical and reporting purposes. A copy of the randomization assignment will be retained at each clinical site by unblinded personnel and will be available to FDA or other regulatory agency investigators at the time of site inspection to allow for verification of the treatment identity of each subject.

3.3. Blinding and Procedures for Unblinding the Study

This is a double-blind study, thus Sponsor, CRO, assessor site staff, study monitors, and subjects will be blinded to the randomization scheme. The packaging of the study drug products will be similar in appearance to make difference in treatment less obvious to the subjects. Blank, opaque diaper labels will be applied to each study tube for maintenance of study blinding. Each tube will be packaged in individualized cartons. Neither the Investigator nor the subject should be able to identify the received treatment. The dispensed investigational product will NOT be opened by the index subject and their family members at the study center.

The blinding code must not be broken except in emergency situations for which the identification of the study treatment of a subject is required by the Investigator to complete a serious adverse event report. In such situations, the Medical Monitor or the Investigator will use the Unblinded Treatment List in order to unblind the treatment for the individual subject. Unblinded information will be held by designated individual(s), and the date and reason for breaking the blind must be recorded.

The Medical Monitor must be contacted by telephone prior to unblinding but no later than 24 hours after unblinding. As the study is blinded, the Investigator should promptly document and explain to the Sponsor any premature unblinding (e.g., accidental unblinding, unblinding due to a serious adverse event) of the investigational product(s). Every effort should be made to avoid unblinding extra study personnel.

3.4. Handling of Data

3.4.1. Examination of Subject Subsets

The primary and secondary efficacy endpoints will be summarized separately using descriptive statistics by treatment group and study day, where appropriate. No formal statistical testing will be utilized.

3.4.2. Missing Data

Every effort will be made to obtain required data at each scheduled evaluation from all subjects who have been randomized. In situations where it is not possible to obtain all safety data, imputation of missing data will not be conducted. A Last-Observation-Carried-Forward imputation method for missing efficacy data will be used for the mITT population.

3.4.3. Definitions and Terminology

Treatment Day 1 (Baseline)

Treatment Day 1 is the day that study treatment is first initiated.

Study Day

Study Day is defined relative to study treatment initiation (Study Day 1). Thus, the study day of an event is calculated as:

Study
$$Day = event date - date of Study Day 1 + 1$$
.

Days on Study

Days on Study is the number of days from Study Day 1 to the date of study completion or early termination as recorded on the study termination eCRF.

End of Treatment

For efficacy assessments, end of treatment is defined as the last non-missing assessment taken prior to discontinuation of study treatment.

Concomitant Medications

Concomitant medications are those medications taken on or after the initiation of study treatment. This definition includes prescription and all over-the-counter (OTC) medications and all dietary supplements.

CONFIDENTIAL

Previous medications are those medications taken within the 30 days and stopped prior to the initiation of study therapy.

Treatment-Emergent Adverse Event

A treatment-emergent adverse event is defined as any adverse event occurring on or after the initiation of study treatment. For the purpose of defining treatment-emergent adverse events, it is assumed that an adverse event which was reported to have started on Treatment Day 1 without an associated onset time may have occurred after the initiation of study treatment. Hence, adverse events occurring on Treatment Day 1 are assumed to be treatment-emergent.

3.5. Planned Analyses

A final analysis is planned after the last subject completes or discontinues the study, and the resulting clinical database has been cleaned, quality checked, and locked.

4. ANALYSIS POPULATIONS

The populations defined for analysis will include the modified intent-to-treat (mITT), per-protocol (PP), and the safety population.

Safety Population includes all subjects who were randomized and dispensed treatment. This is the population that will be used for the safety assessments.

Modified Intent-to-Treat (mITT) Population includes all Index subjects who met all inclusion/exclusion criteria, were randomized, dispensed treatment, and had at least one post-treatment efficacy evaluation. This is the primary population for determination of the superiority of the active treatments over placebo.

Per-Protocol (PP) Population includes all mITT subjects who applied their dispensed treatment, had no protocol deviations which could have interfered with the accurate assessment of treatment efficacy, and returned for the Day 15 visit within the allowed window. This is the primary population for the efficacy comparisons between the two active treatment groups.

Subjects whose condition worsens and require alternate or supplemental therapy for the treatment of head lice during the study will be discontinued, included in both the mITT and PP population analyses as treatment failures. Subjects who discontinue early for reasons other than treatment failure will be excluded from the PP population, but included in the mITT population. Last Observation Carried Forward (LOCF) will be used to impute any missing endpoints.

Efficacy analyses will be performed on both the per-protocol population and the mITT population. Safety analyses will be performed using the Safety population as defined.

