7.3.4 Final Study Visit

Final Study Visit Day 15 (Visit 5) (+/- 3 days)

- Record adverse events as reported by participant or observed by investigator.
- Perform vital signs, results of examinations, and other assessments.
- Concomitant and prohibited medication review.
- Collect urine sample for pregnancy testing for any index subject of child bearing potential.
- Perform assessment for living head lice on index subject for visual confirmation of infestation for a minimum of 15 minutes.
- Record Subject Self-Assessment for index subjects.
- Perform skin/scalp irritation and ocular irritation for index subjects and record results on Site Assessment form.
- Provide rescue standard of care treatment for any index subjects requiring additional treatment.

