7.6 Rescue Medications, Treatments, and Procedures

If live lice are present on Day 2, Day 8 or Day 15, the subject will receive an over-the-counter (OTC) rescue treatment for head lice and their study participation will be considered complete and will be considered a treatment failure, with subjects to be considered in both the mITT and PP population.

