5.2.3. Secondary Efficacy Endpoints

The secondary efficacy endpoint is the number and percentage of all index subjects who are licefree at Day 2. Descriptive statistics (number of subjects, number of subjects cured, and proportion cured) for the secondary efficacy variable will be tabulated by treatment group and population (mITT and PP).

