8. TABLES, LISTINGS AND FIGURES

Tables

- 1. Summary of Subject Enrollment and Disposition.
- 2. Summary of Subject Demographics at Screening (mITT population).
- 3. Summary of Subject Demographics at Screening (PP Population).
- 4. Summary of Medical History/Other Concomitant Illness at Screening.
- 5. Summary of Physical Exam Abnormalities.
- 6. The Difference in proportion of patients that are identified as cured on Study Day 15 (Visit 5) Treated with Ivermectin and Sklice (mITT population).
- 7. The Difference in proportion of patients that are identified as cured on Study Day 15 (Visit 5) Treated with Ivermectin and Sklice visit (PP population).
- 8. The Difference in proportion of patients that are identified as cured on Study Day 15 (Visit 5) Treated with Ivermectin Vs Placebo and Sklice Vs Placebo (mITT population).
- 9. The Difference in proportion of patients that are identified as cured on Study Day 15 (Visit 5) Treated with Ivermectin Vs Placebo and Sklice Vs Placebo (PP population).
- 10. Summary of Head Lice visual examination at each visit (mITT population).
- 11. Summary of Head Lice visual examination at each visit (PP Population).
- 12. The Difference in proportion of patients that are identified as cured on Study Day 2 (Visit 3) Treated with Ivermectin and Sklice (mITT population).
- 13. The Difference in proportion of patients that are identified as cured on Study Day 2 (Visit 3) Treated with Ivermectin and Sklice (PP population).
- 14. The Difference in proportion of patients that are identified as cured on Study Day 2 (Visit 3) Treated with Ivermectin Vs Placebo and Sklice Vs Placebo (mITT population).
- 15. The Difference in proportion of patients that are identified as cured on Study Day 2 (Visit 3) Treated with Ivermectin Vs Placebo and Sklice Vs Placebo (PP population).
- 16. Summary of self-assessment of itching and stinging/ burning sensations at each visit (mITT population).
- 17. Summary of self-assessment of itching and stinging/ burning sensations at each visit (PP population).
- 18. Summary of change of self-assessment of itching and stinging/ burning sensations from baseline at each visit (mITT population).
- 19. Summary of change of self-assessment of itching and stinging/ burning sensations from baseline at each visit (PP population).
- 20. Summary of local skin/scalp irritation assessment at each visit (mITT population).
- 21. Summary of local skin/scalp irritation assessment at each visit (PP population).

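### The only Per-Protocol set requires an in-window Day 15 visit, so a missed or late final visit removes a child from the Day 2 analysis only if that child was lice-free at Day 2

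*SAP*

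**What the plan says.** Protocol 10.2 and SAP 4 define a single PP set. Besides applying the treatment and having no interfering deviation, a member must have "returned for the Day 15 visit within the allowed window"; Protocol 7.3.4 sets that window at 3 days either side of Day 15. SAP 4 adds: "Subjects who discontinue early for reasons other than treatment failure will be excluded from the PP population". No separate set is defined for Day 2.

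Treatment failures are handled differently. Protocol 7.3.3 withdraws a child found with live lice at Day 2. Protocol 7.6 says that a child with live lice at Day 2, 8 or 15 "will be considered a treatment failure, with subjects to be considered in both the mITT and PP population". SAP 4 likewise has children who need other lice therapy "included in both the mITT and PP population analyses as treatment failures". A failure therefore needs no Day 15 visit to be in PP.

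The same set is used for the Day 2 endpoint. SAP 5.2.3 tabulates that endpoint in mITT and PP. The title of SAP Table 13 begins "The Difference in proportion of patients that are identified as cured on Study Day 2 (Visit 3) Treated with Ivermectin and Sklice (PP population". Table 15 is the PP comparison of each active with placebo at Day 2, and Figure 2 plots the PP proportions at Days 2 and 15. Tables 12 and 14 give the same Day 2 comparisons in mITT. SAP 4 names PP the primary set for efficacy comparisons between the two actives and makes no exception for Day 2.

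**The concern.** Membership of the Day 2 PP analysis depends on attendance up to two weeks after the outcome was observed, and that dependence runs only one way. A child who used the lotion properly, came at Day 2 and was lice-free can be removed for a later absence. A child with live lice at Day 2 cannot be, because that child has no later visits to miss. Selection of this kind lowers the PP lice-free rate and does not average out as the sample grows. If non-return differs between Test and Reference, it also creates a Day 2 difference that is not a treatment effect, in the population the plan treats as primary for that comparison.

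**Working it through.** **The plan's own figure.** Protocol 10.5 and SAP 3.1 claim at least 80% power with 280 mITT subjects (120:120:40) and 252 PP (108:108:36). A simulation of 500,000 trials, with true cure rates of 67%, 67% and 27%, the SAP 5.2.2 interval in PP and continuity-corrected Z-tests in mITT, gives joint success of 81.5% to 81.6% with PP size fixed at 108 per active arm, and 81.3% with a binomial PP size. The claim is reproduced. Day 2 is not part of the success definition, so nothing below affects it.

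**Who is counted at Day 2 in PP** (other PP conditions being met):

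| At Day 2 | Afterwards | In the Day 2 PP analysis |
|---|---|---|
| Live lice | Withdrawn that day | Yes, as a failure |
| Lice-free | Live lice at Day 8 | Yes |
| Lice-free | No failure, Day 15 visit in window | Yes |
| Lice-free | No failure, Day 15 visit missed or out of window | No |

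Only the last row is lost, and it contains only Day 2 successes.

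**Formula.** Let c be the true Day 2 lice-free proportion and d the share of Day 2 lice-free children who fall in the last row. The numerator shrinks from c to c(1−d) and the denominator from 1 to 1−cd:

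PP rate = c(1−d)/(1−cd); fall = c − PP rate = cd(1−c)/(1−cd).

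Both c and d are assumptions. The documents give no Day 2 rates. The nearest figures for d are the 10% dropout in Protocol 5.4 and the 10% mITT-to-PP loss in SAP 3.1. The values 67% and 27% are the plan's Day 15 rates, borrowed here only as scenarios.

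**Single arm, d = 10%:**

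| c | PP rate | Fall (points) |
|---|---|---|
| 95% | 0.855/0.905 = 94.5% | 0.5 |
| 90% | 0.810/0.910 = 89.0% | 1.0 |
| 80% | 0.720/0.920 = 78.3% | 1.7 |
| 67% | 0.603/0.933 = 64.6% | 2.4 |
| 40% | 0.360/0.960 = 37.5% | 2.5 |
| 27% | 0.243/0.973 = 25.0% | 2.0 |

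The fall peaks near c = 50% (0.025/0.950 = 2.6 points) and shrinks on either side.

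**Test versus Reference, equal true rates.** Equal d gives equal PP rates and no shift. With d = 5% in one arm and 15% in the other:
- c = 90%: 0.855/0.955 − 0.765/0.865 = 89.5% − 88.4% = 1.1 points.
- c = 80%: 0.760/0.960 − 0.680/0.880 = 79.2% − 77.3% = 1.9 points.

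**Active versus placebo, common d = 10%:**
- 90% and 40%: the difference goes from 50 to 89.0 − 37.5 = 51.5 points.
- 67% and 27%: it goes from 40.0 to 39.7 points (64.63 − 24.97).

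The direction depends on the rates.

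**The case against.** The strongest reply is that this hardly matters. The endpoint is secondary and outside the success definition. Tables 12 and 14 show the same Day 2 comparisons in mITT, which has no Day 15 condition, and mITT is definitive for superiority (Protocol 10.4.2, SAP 5.2.2), so Table 15 is only supportive. Two blinded active arms need not differ in non-return. One PP set with a constant denominator across visits is a defensible convention. SAP 5.2.4, which carries the primary procedures over to the secondary endpoint, names Visit 4 (Day 14), which is neither Day 2 nor Day 8; that the arms are compared at Day 2 in PP rests on Tables 13 and 15 and on the title of Protocol 10.4.2. All of this stands, and it limits the point's weight. It does not remove the selection from Tables 13 and 15 and Figure 2.

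Four stronger readings are tempting, and the documents do not support them.

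- **The active-placebo difference is inflated.** The 67%/27% scenario reduces it slightly. A rise from 50 to 55.6 points can be produced by taking 10% of each whole arm from lice-free children at 90% and 40%: 96/108 = 88.9% and 12/36 = 33.3%. That implies losing 12 of 108 lice-free active children (11%) but 4 of 16 lice-free placebo children (25%), an imbalance that nothing in the plan suggests.
- **The bias is greatest where the true rate is low.** It is greatest near one half; at c = 27% it is smaller than at 67%.
- **The Day 2 interval is 5% wider than it need be.** √(120/108) = 1.054 is an upper bound. The 10% loss also covers non-application and interfering deviations, which a Day 2 set would still exclude.
- **Day 2 failures always stay in PP.** This is exact for Day 15 attendance. The other PP conditions might remove a failure, although Protocol 7.6 and SAP 4 state no such exception.

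**Conclusion.** The point holds as a modest, outcome-dependent selection in the Day 2 PP analysis. In any arm that has some Day 2 failures and loses some lice-free children later, the Day 2 PP rate is biased downward: about 0.5 to 2.5 points over c = 95% to 40% if d is 10%. The Test-Reference difference moves mainly if non-return differs by arm, by about 1.1 to 1.9 points (c = 90% to 80%) under an assumed 5% versus 15% loss, which is small against the 20-point margin. No direction can be claimed for the active-placebo difference. All these sizes rest on assumed Day 2 rates and losses. The Day 15 analysis and the sample size are untouched. It is worth correcting because SAP 4 makes PP primary for Test versus Reference without excepting Day 2, and the correction costs little: a cheap improvement.

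**What to change.** In SAP 4, define a Day 2 PP set: mITT subjects who applied the dispensed treatment, had no interfering deviation up to Day 2, and had a Day 2 evaluation within the allowed window, with no Day 15 condition. Apply these conditions alike to infested and lice-free children. Use the set for Tables 13 and 15 and the Day 2 part of Figure 2. Leave the Day 15 PP set and the mITT tables as they are.

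The Day 2 window must be reconciled first. Protocol 7.3.3 allows one day either side, while the schedules in Protocol 16.1 and SAP 1.2 require the visit within 24 hours of treatment. The sponsor should settle which applies before the set is programmed.

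The cost is one sentence in the SAP and one population flag. The downside is that Day 2 and Day 15 PP tables will have different denominators, which a footnote should explain. Make the change before database lock and unblinding, so that it cannot look data-driven.
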